#### **4.4.3.2. Analysis Methods**

The number of participants (and percentages) fulfilling the secondary endpoints in both groups will be calculated and graphically depicted with bar plots.

For all 3 secondary efficacy endpoints an exact Poisson model, as described in the primary efficacy analysis (see Section 4.4.2.2) will be performed, based on the PPE population. The 95% 2-sided CI for the VE (1-relative risk rate) will be calculated from these regression models and

graphically depicted with forest plots. Moreover, the VE (=1- relative risk) will also be calculated without taking the strata into account, and the 95% 2-sided CI will be based on the exact binomial 95% 2-sided CI ([Attachment 6](#)).

Poisson models will be executed also for the subgroups defined in Section 2.4 only for the first occurrence of any RT-PCR-confirmed RSV disease.

In case the Poisson model for one of the above analyses does not converge, the model for the considered analysis will be fitted with only the vaccination group as independent variable.

For participants with any RT-PCR-confirmed RSV disease, the median duration of the ARI episode will be summarized, and time to first occurrence of any RT-PCR-confirmed RSV disease since vaccination per group will be graphically presented with reverse Kaplan Meier curves.

For participants with any RT-PCR-confirmed RSV disease, the different symptom combinations may be summarized.

The PPE set will be used to analyze all secondary exploratory endpoints.

#### 4.4.4. Exploratory Efficacy Variable(s)

##### 4.4.4.1. Definition

Note: For all exploratory endpoints RSV RT-PCR confirmation is defined based on the GeneXpert assay only.

- **First occurrence of any RT-PCR-confirmed RSV A ARI, based on the GenMark assay**

This is defined as any ARI (as defined [above](#)) in combination with an RSV confirmation based on GeneXpert and an RSV A confirmation by GenMark in at least one of the samples taken up to 7 days after the onset of the ARI episode or during the ARI episode, see Section 4.4.2.1.2 (one positive sample is sufficient).

- **First occurrence of any RT-PCR-confirmed RSV A ARI, based on the DDL assay**

This is defined as any ARI (as defined [above](#)) in combination with an RSV confirmation based on GeneXpert and an RSV A confirmation by DDL in at least one of the samples taken up to 7 days after the onset of the ARI episode or during the ARI episode, see Section 4.4.2.1.2 (one positive sample is sufficient).

- **First occurrence of any RT-PCR-confirmed RSV B ARI, based on the GenMark assay**

This is defined as any ARI (as defined [above](#)) in combination with an RSV confirmation based on GeneXpert and an RSV B confirmation by GenMark in at least one of the samples taken up to 7 days after the onset of the ARI episode or during the ARI episode, see Section 4.4.2.1.2 (one positive sample is sufficient).

- **First occurrence of any RT-PCR-confirmed RSV B ARI , based on the DDL assay**

This is defined as any ARI (as defined [above](#)) in combination with an RSV confirmation based on GeneXpert and an RSV B confirmation by DDL in at least one of the samples taken up to 7 days after the onset of the ARI episode or during the ARI episode, see Section [4.4.2.1.2](#) (one positive sample is sufficient).

- **First occurrence of RT-PCR-confirmed RSV-A-mediated LRTD according each case definition, based on the GenMark assay**

This is defined similarly as the primary endpoint (See Section [4.4.2.1](#)) but taking into account only RSV confirmation based on GeneXpert and RSV A confirmation by GenMark in at least one of the samples taken up to 7 days after the onset of the ARI episode or during the ARI episode, see Section [4.4.2.1.2](#) (one positive sample is sufficient).

- **First occurrence of RT-PCR-confirmed RSV-A-mediated LRTD according each case definition, based on the DDL assay**

This is defined similarly as the primary endpoint (See Section [4.4.2.1](#)) but taking into account only RSV confirmation based on GeneXpert and RSV A confirmation by DDL in at least one of the samples taken up to 7 days after the onset of the ARI episode or during the ARI episode, see Section [4.4.2.1.2](#) (one positive sample is sufficient).

- **First occurrence of RT-PCR-confirmed RSV-B-mediated LRTD according each case definition, based on the GenMark assay**

This is defined similarly as the primary endpoint (See Section [4.4.2.1](#)) but taking into account only RSV confirmation based on GeneXpert and RSV B confirmation by GenMark in at least one of the samples taken up to 7 days after the onset of the ARI episode or during the ARI episode, see Section [4.4.2.1.2](#) (one positive sample is sufficient).

- **First occurrence of RT-PCR-confirmed RSV-B-mediated LRTD according each case definition, based on the DDL assay**

This is defined similarly as the primary endpoint (see Section [4.4.2.1](#)) but taking into account only RSV confirmation based on GeneXpert and RSV B confirmation by DDL in at least one of the samples taken up to 7 days after the onset of the ARI episode or during the ARI episode, see Section [4.4.2.1.2](#) (one positive sample is sufficient).

- **First occurrence of any RT-PCR-confirmed ARI, other than RSV**

Midturbinate nasal swabs of all ARI episodes may also be tested against other respiratory pathogens. For each one of the following respiratory diseases, the first occurrence of an RT-PCR confirmed disease is defined as any ARI (as defined [above](#)) in combination with an RT-PCR confirmation for the specific disease (as defined in Section [4.4.2.1.2](#)). Based on the results from the GenMark Respiratory Panel and/or the GeneXpert panel, RT-PCR confirmed ARI for the respective diseases will be defined as follows:

- **Influenza:** at least one RT-PCR results above LLOQ for at least one influenza strain (A, A H1, A H3, A 2009 H1N1, B), for either the GenMark Respiratory Panel or the GeneXpert panel
- **Parainfluenza:** at least one RT-PCR results above LLOQ for at least one parainfluenza strain (Virus 1, Virus 2, Virus 3)
- **Human Metapneumovirus:** at least one RT-PCR results above LLOQ
- **Human Rhinovirus:** at least one RT-PCR results above LLOQ
- **Adenovirus B/E:** at least one RT-PCR results above LLOQ
- **Adenovirus C:** at least one RT-PCR results above LLOQ
- **Adenovirus B/E and/or C:** at least one RT-PCR results above LLOQ for either strains

Note: this endpoint will be only analyzed if the GenMark panel has run for all ARIs. This is not yet planned for the primary analysis.

- **First occurrence of any RT-PCR-confirmed ARI, other than RSV, according to each case definition**

For each one of the respiratory diseases tested (influenza, parainfluenza, human metapneumovirus, human rhinovirus, adenovirus B/E, adenovirus C and adenovirus B/E and/or C), the first occurrence of an RT-PCR confirmed disease according to the case definitions is defined similar to the primary endpoint (see Section 4.4.2.1), but instead of an RSV RT-PCR confirmation, an RT-PCR confirmation is needed based on the GenMark Respiratory Panel and/or the GeneXpert panel for the different diseases.

Note: this endpoint will be only analyzed if the GenMark panel has run for all ARIs. This is not yet planned for the primary analysis.

- **First occurrence of potential complications of ARI**

This is defined as the first occurrence of any complication linked to an ARI (as defined [above](#)) episode.

- **First occurrence of potential complications of respiratory disease linked to an RT-PCR confirmed RSV ARI**

This is defined as the first occurrence of any complication linked to any RSV-confirmed disease (see Section 4.4.3.1)

- **First occurrence of hospitalization linked to an ARI**

This is defined as the first occurrence of a hospitalization linked to an ARI (as defined [above](#)) episode. Hospitalization defined in section 12.

- **First occurrence of hospitalization linked to an RT-PCR confirmed RSV ARI**

This is defined as the first occurrence of a hospitalization linked to any RT-PCR-confirmed RSV disease (see Section 4.4.3.1). Hospitalization defined in section 12.

- **First occurrence of RT-PCR-confirmed RSV-mediated LRTD according an ordinal case definition**

The ordinal case definition is defined as follows:

**Table 9: Ordinal Case Definition**

Ordinal Case definition	Ordinal variable	Participants fulfilling
≥3 symptoms of LRTI (new onset or worsening), in combination with confirmation of RSV by RT-PCR in one or more of the midturbinate nasal swabs, or in the sputum sample (when available) (GeneXpert or local lab)	3	Case Definition 1, 2 and 3
2 symptoms of LRTI (new onset or worsening), in combination with confirmation of RSV by RT-PCR in one or more of the midturbinate nasal swabs, or in the sputum sample (when available) (GeneXpert or local lab)	2	Case Definition 2 and 3 (not Case definition 1)
1 symptom of LRTI (new onset or worsening) combined with a systemic symptom, in combination with confirmation of RSV by RT-PCR in one or more of the midturbinate nasal swabs, or in the sputum sample (when available) (GeneXpert or local lab)	1	Only Case Definition 3 (not Case definitions 1 and 2)
Other	0	No case definition

For subjects fulfilling at least one case definition, the follow-up time is defined as the time between vaccination and the occurrence of the first event with the highest ordinal variable (the event corresponding to the strictest case definition). For non-cases, it is the time between vaccination and the end of season visit. In case the end of season visit is missing then the 15th of May 2020 will be used as end of season. However, for participants that discontinued before having an event, follow-up time is the time between vaccination and the date of last contact (date of discontinuation).

- **Determination of oxygen saturation during clinical assessment during ARI episodes for subjects with an ARI**
- **Determination of oxygen saturation during clinical assessment during ARI episodes for subjects with an RT-PCR confirmed RSV ARI**
- **First occurrence of an RT-PCR confirmed RSV Lower Respiratory Infection (LRI) assessed as at least mild by the CEC**
- **First occurrence of an RT-PCR confirmed RSV LRI assessed as at least moderate by the CEC.**
- **First occurrence of an RT-PCR confirmed RSV LRI assessed as severe by the CEC.**
- **If the G-ELISA assay is available: Explore the relationship between G-ELISA and RT-PCR confirmed RSV infection. Provided a cut-off for G-ELISA FR is found that is sufficiently sensitive and specific, the following objectives will be explored:**
  - First occurrence of serology-confirmed RSV-mediated LRTD according to each case definition
  - First occurrence of any serology-confirmed RSV ARI

- First occurrence of any serology and/or RT-PCR-confirmed RSV ARI
- First occurrence of serology and/or RT-PCR-confirmed LRTD according each case definition

The analyses to explore a cut-off for G-ELISA FR will be described in more detail in the CoP SAP

- **[EMA Endpoints]: First occurrence of RT-PCR confirmed RSV-mediated LRTD according to the following 2 case definitions:**

- Case Definition 1a: new onset of worsening of  $\geq 3$  LRTI symptoms based on [Table 8](#), and fever (all temperatures  $>37.8^{\circ}\text{C}$ ) or feeling feverish
- Case Definition 2a: new onset of worsening of  $\geq 2$  LRTI symptoms based on [Table 8](#), and fever (all temperatures  $>37.8^{\circ}\text{C}$ ) or feeling feverish

For both these case definitions, dyspnea and decreased oxygen saturation will count as separate LRTI symptoms.

For example, if a participant has a new onset on cough, dyspnea, decreased oxygen saturation and a fever of  $39.0^{\circ}\text{C}$ , this participant fulfils Case Definition 1a.

#### 4.4.4.2. Analysis Methods

For all exploratory efficacy endpoints related to the first occurrence of a disease an exact Poisson model, as described in the primary efficacy analysis (see Section [4.4.2.2](#)) will be performed, based on the PPE population. The 95% exact 2-sided CI for the VE (1-relative risk rate) will be calculated from these regression models and graphically depicted with forest plots. In case of the model does not converge then it will be fitted with only the vaccination group as dependent variable.

For the first occurrence of complications or hospitalizations linked to any ARI and complications or hospitalizations linked to any RT-PCR confirmed RSV disease, the proportion of participants with complications and hospitalizations, will be tabulated separate and an exact Poisson model, as described in the primary efficacy analysis (see Section [4.4.2.2](#)) will be performed, based on the PPE population. The 95% 2-sided CI for the VE (1-relative risk rate) will be calculated from these regression models and graphically depicted with forest plots. In case the Poisson model for one of the above analyses does not converge, the model for the considered analysis will be fitted with only the vaccination group as independent variable.

Complications linked to any ARI and complications linked to any RT-PCR confirmed RSV disease will be summarized by System Organ Class and Preferred Term, per group and per risk level. A summary table including complications with fatal outcomes, complications reported as SAEs and those leading to permanent stop of the vaccination, will also be created. Number of participants with one complication, two complications, three complications or more than 3 complications will also be summarized.

Moreover, for the determination of oxygen saturation the number of subjects (and percentages) with baseline  $\text{SpO}_2 \geq 90\%$  and  $\text{SpO}_2 < 90\%$  during the ARI episode and the number of subjects

(and percentages) with baseline SpO2 <90 and that have a ≥2% decrease during ARI episode will be tabulated per group.

#### 4.4.4.3. The Relationship Between the Primary Endpoints and CEC Evaluation

In order to establish the interrelationship between the primary endpoints and RT-PCR confirmed LRIs considered at least moderate by the CEC, the following analyses will be performed restricted to the placebo group. These analyses will be performed in two subgroups of the PPE set:

- participants with any RT-PCR confirmed RSV disease (see [above](#) for definition)

In each of those subgroups the following will be calculated: the percentage of subjects having an (RT-PCR confirmed RSV) ARI considered at least moderate by the CEC will be shown for:

- participants meeting Case Definition 1 versus participants not meeting any Case Definition
- participants meeting Case Definition 2 (or 1) versus participants not meeting any Case Definition
- participants meeting Case Definition 3 (or 1 or 2) versus participants not meeting any Case Definition

The corresponding odds ratio (and 95% CI) will be shown as well.

In case of limited number of participants not meeting any case definition:

- participants meeting Case Definition 1 versus participants not meeting Case Definition 1
- participants meeting Case Definition 2 (or 1) versus participants not meeting Case Definition 2 (or 1)
- participants meeting Case Definition 3 (or 1 or 2) versus participants not meeting any Case Definition

The corresponding odds ratio (and 95% CI) will be shown as well.

Moreover, the correlation between the 3 case definitions and the RT-PCR confirmed ARIs assessed by the CEC, will be explored with scatterplots.

Finally the results of the CEC evaluation will be used to explore the creation of a severity score (based on RiiQ and clinical assessment data) with a cut-off to classify an RT-PCR confirmed RSV ARI to having an RT-PCR confirmed RSV LRI assessed at least moderate by the CEC (yes/no). Classification trees (or other classification methods), logistic regression models, combinations of these or other techniques might be used to define a score. An optimal cut-off might be identified based on Receiver operating characteristic (ROC) curves, which might be used to calculate a VE.

The PPE set will be used to analyze all efficacy exploratory endpoints.

## 4.5. PATIENT-REPORTED OUTCOMES

### 4.5.1. Respiratory Infection Intensity and Impact Questionnaire (RiiQ™v2)

The RiiQ consists of 4 scales that are scored separately:

- **RiiQ Symptom Scale (Question 1).** Each symptom is rated on the following scale: 0=None, 1=Mild, 2=Moderate, and 3=Severe. Based on this questioner, 4 different total scores 2 areas under the curve (AUC) will be calculated:
  - **Total RiiQ Respiratory and Systemic symptom score** is the mean of all scores.
  - **Total RiiQ Respiratory symptom score** is the mean of 6 symptoms, i.e., 2 URTI symptoms (Nasal congestion and Sore throat) and 4 LRTI symptoms (Cough, Wheezing, Shortness of breath, and Coughing up phlegm/sputum)
  - **Total RiiQ Systemic symptom score** is the mean of 7 systemic symptoms (Headache, Feeling feverish, Neck pain, Body aches and pain, Fatigue/tiredness, Interrupted sleep, and Loss of appetite).
  - **Total RiiQ Case Definition symptom score** is the mean of 4 LRTI symptoms (Cough, Wheezing, Shortness of breath, and Coughing up phlegm/sputum) and 2 systemic symptoms used in the case definitions, fatigue and feeling feverish
  - Moreover, the **AUC** ([Attachment 4](#)) for the change from baseline for the Total RiiQ Respiratory and Systemic symptom score and the Total RiiQ Case Definition symptom score will be calculated.
- **RiiQ Impact Scales (Questions 2 to 4):**
  - **Total RiiQ Impact on Daily Activity score (Question 2)** consists of 7 activities. Ability to perform each activity item is rated on the following scale: 0=No difficulty, 1=Some difficulty, 2=Moderate Difficulty, and 3=Great difficulty. The total score is calculated as the mean of all 7 items (range 0-3).
  - Moreover, the **AUC for the change from baseline for the Total RiiQ Impact on Daily Activity score** will be calculated.
  - **Total RiiQ Impact on Emotions scale (Question 3)** consists of rating 4 negative emotions, rated on the following scale: 0=Not at all, 1=Somewhat, 2=Moderately, and 3=Extremely. The total score is calculated as the mean of all 4 items (range 0-3).
  - **Total RiiQ Impact on Relationships scale (Question 4)** consists of 5 problems that a respiratory infection may cause in relationships with others, rated on the following scale: 0=Not at all concerned, 1=Somewhat concerned, 2=Moderately concerned, and 3=Extremely concerned. The total score is calculated as the mean of all 5 items (range 0-3).

**Note 1:** Total scores will be calculated based on the number of assessments completed by the participant and in cases where more than 50% of the items needed to calculate the score is not collected (reported as ‘Not done’), then the value for that score will be set to missing. For example, if a participant has responded to only 11 out of the 13 RiiQ symptom scale questions the ‘Total RiiQ Respiratory and Systemic symptom’ score will be the mean of the 11 available

questions. If the participant has only completed 6 or less of the questions, then the Total RiiQ Respiratory and Systemic symptom score will be set to missing.

**Note 2:** For outputs where the end of season visit is presented, in case there are multiple end of season visits, the worst score across the different scheduled and unscheduled visits will be presented.

#### 4.5.1.1. Analysis Methods

RiiQ scores will be analyzed based on the PPE set, with a major focus participants with any RT-PCR disease (see [above](#) for definition) .

For the **total scores**, number of observations, mean, standard error, median, first and third interquartile will be tabulated and means with standard errors will be graphically presented per group and time point for changes from baseline. Moreover, the relationship of the baseline total scores and the worst score reported during the ARI episode will be explored with scatterplots. Furthermore, descriptive statistics of the baseline, the end of season and the change between these two timepoints will be calculated for all participants based on the PPE set, for participants with any RT-PCR-confirmed RSV disease and for participants meeting each of the primary endpoints separately, based on the PPE set.

For the **AUCs** number of observations, median, first and third quartile (q1, q3), minimum and maximum will be calculated and graphically presented with boxplots per group. Scatterplots of the AUC values versus the duration of the ARI episodes will also be created.

**Note 1:** Everything reported until the resolution of an ARI will be used.

In case two or more assessments are reported at the same day (for example ARI Day 3-5 eDiary and eDevice or two assessments at the same device) then the worst total score will be used. The same applies for the AUC calculations too.

In case a participant experiences two or more ARIs (based on the ‘Any ARI’ definition, Section 4.4.3.1) during the study then the following rules will be followed in identifying which ARIs data will be used:

- If all fulfil a case definition, then data from the RT-PCR confirmed RSV disease fulfilling the strictest definition will be used (case definition 1 > case definition 2 > case definition 3)
- If only one fulfils a case definition, then those data will be used
- If none fulfils a case definition or all fulfil the same case definition, then data from the first RT-PCR confirmed RSV disease will be used.
- If none is a RT-PCR confirmed RSV disease, then use:
  - the ARI that fulfils the strictest case definition based on symptoms only (case definition 1 > case definition 2 > case definition 3) Or
  - the first ARI, in case 2 or more fulfil the same case definition on symptoms only or in case they do not fulfil any case definition on symptoms only.

Note 2: For outputs were only planned visits (ARI Day 3-5, ARI Day 29, End of season) are presented, the worst across the different scheduled and unscheduled visits will be presented per visit.

#### 4.5.2. Patient Global Impression Scores

- **Patient Global Impression of Health (PGI-H).** Participants report their overall impression of their health status today on the following scale: 0=Very poor, 1=Poor, 2=Fair, 3=Good, 4=Very good.
- **Patient Global Impression of Severity (PGI-S).** Participants rate the severity of their respiratory illness on the following scale: 0=I feel fine (no respiratory illness), 1=I feel a little ill, 2=I feel very ill, 3=I feel extremely ill.
- **Patient Global Impression of Change (PGI-C).** Participants rate the amount of change in their health each day during an ARI episode on the following scale: -3= much better, -2=somewhat better, -1=A little better, 0=About the same, 1=A little worse, 2=somewhat worse, 3= much worse
- **Return to Usual Health.** Participants are being asked whether they have returned to their usual health after developing symptoms suggesting an ARI.
- Number of days a participant took to return to its usual health: This is counted based on the Return to Usual Health question.
  - In case a participant indicated he returned to its usual health (based on the ‘Return to usual health’ question) on the last day he completed this questionnaire during the considered episode, this is calculated as: *the first day of a series where the participant answered consecutively ‘yes’ to the ‘Return to usual health question’ (with no intermittent ‘no’ answers) - the ARI start date based on the CRF+1* . For the Kaplan-Meier curve this is considered an event.
  - In case a participant indicated he did not return to its usual health (based on the ‘Return to usual health’ question) on the last day he completed this questionnaire during the considered episode, this is calculated as: *the date of the last reply- the ARI start date based on the CRF + 1*. For the Kaplan-Meier curve this record will be censored.
  - In case a participant never responded to any ‘Return to usual health’ question during an ARI episode then the number of days will be considered missing.

For example, if 2 participants completed the ‘Return to Usual Health’ question only for 8 days as indicated in [Table 10](#). For participant 1 the number of days to return to usual health is 5 (15/11/2019- 11/11/2019 + 1) and this will be considered an event. For participant 2, the number of days to return to usual health is 8 (18/11/2019- 11/11/2019 + 1) and this record will be censored.

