#### **4.4.2.1.3. ARI Episode Duration**

The duration of an ARI episode is defined as: *Last day of symptoms above baseline - start date of ARI + 1*. The ARI Day 1 and ARI Day 3-5 visits are always taken into account for the duration if there is a new onset or worsening of a symptom. The ARI Day 29 is taken into account for the duration only if the RiiQ assessments reported by the participants on his/her home device go up to or exceed the ARI Day 29 visit date (actual date). In this case, ARI Day 29 site assessments occurring after this last RiiQ assessment reported by the participants on his/her home device (actual day) are not taken into account for the duration. End of Season as well as Day 365 and Day 730 visits are excluded when determining ARI end dates. Only URTI and LRTI symptoms from clinical assessment and patient reported outcome will be used in calculating the duration of an ARI episode (Table 8).

Moreover, for ARIs with no new onset or worsening of symptoms, duration will not be calculated.

For calculating the ARI duration, the following rules may be used:

- For all ARIs the start dates are reported in the CRF (=CE.CESTDTC where CETERM=ACUTE RESPIRATORY INFECTION and CE.CECAT= ‘’).

- Then a temporary end date for each ARI is created:
  - In case a participant has multiple ARIs, the temporary end date is set as a day before the start of the next ARI.
  - In case a participant has only one ARI, the temporary end date is set as the day of database cut off (15 May 2020).
- Search between the ARI start date and the temporary end date, for the last date the participant had a new onset or worsening of URTI or LRTI symptoms (Table 8), at the RiiQ assessments completed on his /her device and set it as ‘*enddate1*’.
- If the RiiQ assessments, between the ARI start date and the temporary end date, reported by the participants on his/her home device do not reach the actual ARI Day 29 visit date. Search between the ‘ARI Day 1’ and ‘ARI Day 3-5’ visits (both scheduled and unscheduled), for the last date the participant had a new onset or worsening of URTI or LRTI symptoms (Table 8), at the assessments collected during these visits and set it as ‘*enddate2*’.

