- If the RiiQ assessments between the ARI start date and the temporary end date reported by the participants on his/her home device go up to or exceed the ARI Day 29 visit date (actual date). Search between the ‘ARI Day 1’, ‘ARI Day 3-5’ and ‘ARI Day 29’ visits (both scheduled and unscheduled), for the last date the participant had a new onset or worsening of URTI or LRTI symptoms (Table 8), at the assessments collected during these visits (clinical assessments and RiiQ) or at the participants device at home (RiiQ) during these dates and set it as ‘*enddate2*’.
- The ARI episode end date is defined as the maximum between ‘*enddate1*’ and ‘*enddate2*’.
- And the duration is defined as the *end date – ARI start date + 1*

**Note 1:** in case there is no new onset or worsening after the ARI start date then the ARI end date and the duration are considered missing.

**Note 2:** the start date of the ARI is always the date reported in the CE domain, even if the subject started reporting symptoms only later in the diary.

For example, see [Attachment 8](#)

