#### 4.5.2.1. Analysis Methods

Patient global impression scores will be analyzed based on the PPE set, with a major focus participants with any RT-PCR disease (see [above](#) for definition).

For the PGI-H, number of observations, mean, standard error, median, first and third quartile, minimum and maximum will be tabulated and means with standard errors will be graphically presented per group and time point for the change from baseline.

For the PGI-C and PGI-S scores, score, number of observations, mean, standard error, median, first and third quartile, minimum and maximum will be tabulated and means with standard errors will be graphically presented per group and time point.

For the PGI-H, descriptive statistics of the baseline, the end of season and the change between these two timepoints will be calculated for all participants based on the PPE set, for participants with any RT-PCR-confirmed RSV disease and for participants meeting each of the primary endpoints separately, based on the PPE set.

The number (and percentage) of participants answering yes and no in the 'Return to Usual Health' question will be calculated per day.

Moreover, the number of days a participant took to return to its usual health will be summarized and graphically presented with Kaplan Meir curves.

In case two or more assessments are reported at the same day (for example eDiary and eDevice or two assessments at the same device) then the worst PGI score (or when looking to Return to Usual Health, the worst answer to this question) will be used.

In case a participant experiences two or more ARIs during the study the same rule as for the RiiQ will be used.

Note 1: For outputs where only planned visits (ARI Day 3-5, ARI Day 29, End of season) are presented, the worst across the different scheduled and unscheduled visits will be presented per visit.

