#### 5.5.2.1. Analysis Methods

The following analysis will be conducted for any RSV ARI, RSV A ARI and RSV B ARI (based on the DDL assay) and in case of the AUC analyses additionally for RT-PCR-confirmed RSV-A-

mediated LRTD and RT-PCR-confirmed RSV-A-mediated LRTD based on Case Definition 1 occurring during the second or third RSV season and across three RSV seasons.

For the AUCs the number of observations, median, first and third quartile ( $q_1$ ,  $q_3$ ), minimum and maximum will be calculated and graphically presented with boxplots per group.

Moreover, the number of days a participant took to return to its usual health will be summarized and graphically presented with Kaplan Meir curves. Hazard ratios will also be calculated, with a cox proportional hazard model with time to return to usual health as dependent variable and group as independent variable.

In case a participant experiences two or more RSV ARIs during the three RSV seasons, the same rule will apply similar to a participant experiencing two or more ARIs during the same season (see Section 4.5.1.1).

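### Time to return to usual health: a direct summary of the number of days mixes recovery times with censoring times, and the answer window that decides recovery is not tied to a date

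*SAP*

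**What the plan says.** - **Status and time (SAP 4.5.2).** Status comes from the answer given "on the last day he completed this questionnaire during the considered episode". If it is *yes*, the time runs from the CRF start date of the ARI to the first day of the final unbroken run of *yes* answers: "For the Kaplan-Meier curve this is considered an event". If it is *no*, the same variable takes the day of the last answer: "For the Kaplan-Meier curve this record will be censored".
- **Use in season one (SAP 4.5.2.1).** The plan says that "the number of days a participant took to return to its usual health will be summarized" and also plotted as Kaplan-Meier curves.
- **Use in later seasons (SAP 5.5.2.1).** The same summary and curves are planned for the second and third seasons and across all three. Hazard ratios are added "with a cox proportional hazard model with time to return to usual health as dependent variable and group as independent variable".
- **Episode end (SAP 4.4.2.1.3).** This is the only place where an end date is derived. Duration is "Last day of symptoms above baseline - start date of ARI + 1". "The ARI episode end date is defined as the maximum between" two candidate dates, each found by a search "for the last date the participant had a new onset or worsening of URTI or LRTI symptoms". Systemic symptoms do not extend the episode.

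**The concern.** There are two separate problems.

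First, one variable holds two different quantities. For a recovered participant it is a recovery time. For a participant who has not recovered it is only a time that recovery exceeds. Section 4.5.2 protects against confusing them in the Kaplan-Meier curve and mentions no other analysis. The two analysis sections then ask for a summary of the number itself without saying how censored records enter. A mean or median of the raw values would be too low, and the error grows with the share of participants still unrecovered at their last answer. If that share differs between vaccine and placebo, the group comparison is distorted too.

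Second, Section 4.5.2 does not say when the answer window closes. The derived ARI end date is the obvious candidate for a programmer: Section 4.16 already uses the episode duration as the denominator for diary compliance. That date is the last day with a respiratory symptom above baseline, whereas a participant may well first report being back to usual health after it. A cut there could remove the answers that record recovery, and the Kaplan-Meier curves and the Cox hazard ratio would inherit the result.

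**Working it through.** **1. Reproduce the plan's example (4.5.2 and Table 10).** The ARI starts on 11/11/2019, and day = date − start + 1.

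- Participant 1 answers N N Y N Y Y Y Y. The last answer is *yes*, and the final run of *yes* starts on 15/11: 15 − 11 + 1 = 5, an event.
- Participant 2 answers N N Y Y Y N N N. The last answer is *no*, on 18/11: 18 − 11 + 1 = 8, censored.

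Both match the SAP when all eight answers are used.

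**2. Direct summary of those values.** The raw mean is (5 + 8) / 2 = 6.5 days. Participant 2 answered *no* on day 8, so sustained recovery falls on day 9 at the earliest, and the true mean is at least (5 + 9) / 2 = 7 days. In general each censored value is below the recovery time it stands for, so the mean and every quantile of the raw values are at or below those of the recovery times. This step does not depend on how the answer window is read.

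**3. Sensitivity of Table 10 to the window.** Table 10 has no symptom data, so the last symptomatic day is varied here as an assumption and answers after it are dropped.

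| Last symptomatic day | Participant 1 | Participant 2 |
|---|---|---|
| 1 | day 1, censored | day 1, censored |
| 2 | day 2, censored | day 2, censored |
| 3 | day 3, event | day 3, event |
| 4 | day 4, censored | day 3, event |
| 5 | day 5, event | day 3, event |
| 6 | day 5, event | day 6, censored |
| 7 | day 5, event | day 7, censored |
| 8 | day 5, event | day 8, censored |
| No cut (SAP result) | day 5, event | day 8, censored |

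A cut can lose a recovery (participant 1 at day 4). It can also create one: participant 2, cut at days 3 to 5, counts as recovered on day 3 although the last three answers are *no*.

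**4. Diaries can outlast the derived end date (Attachment 8, Example 1).** The ARI starts on 10/11 and symptom-questionnaire entries on the home device run to 16/11. The derived end is 14/11, or 11/11 in the variant without symptoms at the Day 3-5 visit. The example shows no Return to Usual Health answers. Assume daily answers, *no* up to the derived end and *yes* from the next day.

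- End 14/11: all answers give an event at 15 − 10 + 1 = day 6; the cut gives censoring at 14 − 10 + 1 = day 5.
- End 11/11: all answers give an event at 12 − 10 + 1 = day 3; the cut gives censoring at 11 − 10 + 1 = day 2.

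**5. Size if the cut were applied.** Let p be the share of recovering participants whose sustained *yes* starts after the derived end date. The share kept as events is 1 − p. The SAP gives no value for p; 25%, 50%, 75% and 100% leave 75%, 50%, 25% and 0%.

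For the Kaplan-Meier median, assume an exponential last symptomatic day with median 8 days, where a share q = 1 − p says *yes* on that day and the rest on the next. The event hazard is then q times the total hazard, and the Kaplan-Meier median is 8 / q: 16 days at q = 50% and about 27 days at q = 30%, against a true median of 8 to 9 days. These inputs are illustrative only.

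**The case against.** The strongest objection concerns the window. Section 4.5.2 never says that answers after the derived end date are dropped. It does not cite Section 4.4.2.1.3, it anchors on the CRF start date, and it censors at the last answer rather than at an episode end. The word *considered* can simply identify which ARI is meant, since Section 4.5.2.1 applies a selection rule when a participant has several. Section 4.4.2.1.1 speaks of the ARI episode as the period in which the daily diary is filled in. Table 10 uses all eight answers. All of this stands: the reading without a cut fits the text more easily.

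A reader might infer more than the documents support:

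- *That the SAP already censors recovered participants, and that Table 10 shows it.* The cut is one possible reading, not a stated rule. Table 10 has no symptom data and reproduces with every answer included.
- *That under a cut only participants who are still symptomatic could be events.* Attachment 8 shows symptom-free days inside an episode, and the last symptomatic day may come from a site visit alone. Only those whose sustained *yes* starts after the end date would be lost. The censoring would be informative for them, but it has not been shown to be so for everyone.

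On the summary, it can be said that a time with a censoring flag is ordinary practice, that the sentence may mean a Kaplan-Meier summary, and that output details belong in the data presentation specifications. This stands in part, because the text does not order a raw mean or median. But it names censoring for the curve only, calls the value a number of days to return even for someone who has not returned, and does not say that the summary accounts for it.

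**Conclusion.** The concern about the summary holds on the text as it stands. A direct summary of the number of days combines recovery times with last-answer days and understates time to recovery. The size depends on the censored share, which the SAP does not give; in the two-participant example the raw mean is 6.5 days against at least 7.

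The concern about the window holds as an ambiguity. The window has no stated end, and applying the only derived end date would change event status in both directions. The loss of events would equal the share of participants whose sustained *yes* follows the last respiratory symptom, and that share is unknown. The Kaplan-Meier medians in the working are illustrations under assumed inputs, not estimates for this trial.

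This is a supportive patient-reported outcome. The primary endpoints and the proof-of-concept decision are not touched, but a between-group hazard ratio is planned on this variable, so the clarification is worth making.

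**What to change.** **Sections 4.5.2.1 and 5.5.2.1.** Replace the summary of the raw number of days with the Kaplan-Meier median and quartiles per group, together with the numbers of events and censored records. Say that the censoring flag applies to every analysis of this variable, not only to the curve.

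**Section 4.5.2.** State that all Return to Usual Health answers linked to the selected ARI count, from its CRF start date to the last reply before the next ARI, regardless of the end date in Section 4.4.2.1.3. This agrees with Table 10, and Section 4.4.2.1.3 already uses the day before the next ARI as a temporary boundary.

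**Cost.** About one sentence in each of the three sections, and no new data. There is a small downside: an isolated late *yes* after a gap in the diary may date recovery later than it occurred.
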